**Clinical Study Protocol**  
**Johnson & Johnson Vision**

Visit 1: Spherical Lens Fitting: Phase 1 and 2		
Step	Procedure	Details
1.22	Lens Settling 2	Please wait a total of 10 minutes from final lens insertion to continue.
1.23	Visual Acuity	Record the best corrected Snellen distance visual acuity to the nearest letter (OD, OS, and OU). Subjects must read the smallest line until at least 50% of the letters are read incorrectly. Visual acuity with the study contact lenses must be 20/30 or better OD, OS and OU.
1.24	General Lens Fit Assessment	
Evaluate lens centration, movement on blink, and push-up test for each eye.
 
An unacceptable fit is deemed by one of the following criteria:
 
 
• limbal exposure at primary gaze or with extreme eye movement.
 
• edge lift.
 
• excessive movement in primary and up gaze.
 
• insufficient movement in all three of the following conditions: primary gaze, up gaze, and push-up test.
 
 
Note: if lens fit is unacceptable for either eye, the subject will be discontinued from the study.

Visit 1: Multifocal Lens Fitting: Phase 1 and 2		
Step	Procedure	Details
1.25	Lens Selection	
Assign the study lens (Test or Control) according to the randomization scheme provided by the biostatistician.
 
Select the contact lens power based on the vertex-corrected refraction.
 
Record the test condition.

**Clinical Study Protocol**  
**Johnson & Johnson Vision**

Visit 1: Multifocal Lens Fitting: Phase 1 and 2																																																	
Step	Procedure	Details																																															

 
 	ADD									
 
 	+0.75	+1.00	+1.25	+1.50	+1.75	+2.00	+2.25	+2.50		
 
 Dominant Eye	LOW	LOW	LOW	MID	MID	MID	MID	MID		
 
 Non Dominant Eye	LOW	LOW	LOW	MID	MID	HGH	HGH	HGH		
 
											ADD										+0.75	+1.00	+1.25	+1.50	+1.75	+2.00	+2.25	+2.50		Dominant Eye	LOW	LOW	LOW	MID	MID	MID	MID	MID		Non Dominant Eye	LOW	LOW	LOW	MID	MID	HGH	HGH	HGH	
	ADD																																																
	+0.75	+1.00	+1.25	+1.50	+1.75	+2.00	+2.25	+2.50																																									
Dominant Eye	LOW	LOW	LOW	MID	MID	MID	MID	MID																																									
Non Dominant Eye	LOW	LOW	LOW	MID	MID	HGH	HGH	HGH																																									
1.26	Lens Insertion	
The Investigator or the subject inserts the study lenses. Record the time of lens insertion.
 
Check for lens damage under the slit lamp before proceeding with lens settling.
 
Replace damaged lenses if applicable.
 
Ensure the subject is given a Clinic-only Wear Patient Instruction Guide.
																																															
1.27	Lens Settling 1	
Allow the study lenses to settle for a minimum of 5 minutes.
																																															
1.28	Subjective Best Sphere Over Refraction	
Perform subjective best sphere refraction over the study lenses with a phoropter (adopt the maximum plus to maximum visual acuity (MPMVA) approach) and record the best corrected distance visual acuity to the nearest letter (OD, OS, and OU).
																																															
1.29	Lens Settling 2	
Please wait a total of 10 minutes from final lens insertion to continue.
																																															
1.30	Visual Acuity	
Record the best corrected Snellen distance visual acuity to the nearest letter (OD, OS, and OU). Subjects must read the smallest line until at least 50% of the letters are read incorrectly. Visual acuity with the study contact lenses must be 20/30 or better OD, OS and OU.
																																															

**Clinical Study Protocol**  
**Johnson & Johnson Vision**

Visit 1: Multifocal Lens Fitting: Phase 1 and 2		
Step	Procedure	Details
1.31	General Lens Fit Assessment	
Evaluate lens centration, movement on blink, and push-up test for each eye.
 
An unacceptable fit is deemed by one of the following criteria:
 
 
• limbal exposure at primary gaze or with extreme eye movement.
 
• edge lift.
 
• excessive movement in primary and up gaze.
 
• insufficient movement in all three of the following conditions: primary gaze, up gaze, and push-up test.
 
 
Note: if lens fit is unacceptable for either eye, the subject will be discontinued from the study.

Visit 1: Toric Lens Fitting: Phase 2		
Step	Procedure	Details
1.32	Lens Selection	
Assign the study lens (Test or Control) according to the randomization scheme provided by the biostatistician.
 
Select the contact lens power based on the vertex-corrected refraction.
 
Record the test condition.

1.33	Lens Insertion	
The Investigator or the subject inserts the study lenses. Record the time of lens insertion.
 
Check for lens damage under the slit lamp before proceeding with lens settling.
 
Replace damaged lenses if applicable.
 
Ensure the subject is given a Clinic-only Wear Patient Instruction Guide.

1.34	Lens Settling 1	
Allow the study lenses to settle for a minimum of 5 minutes. For toric lenses, ensure the lens orientation has stabilized before continuing.

**Clinical Study Protocol**  
**Johnson & Johnson Vision**

Visit 1: Toric Lens Fitting: Phase 2		
Step	Procedure	Details
1.35	Subjective Best Sphere Over Refraction	Perform subjective best sphere refraction over the study lenses with a phoropter (adopt the maximum plus to maximum visual acuity (MPMVA) approach) and record the best corrected distance visual acuity to the nearest letter (OD, OS, and OU).
1.36	Lens orientation	Measure the lens orientation in each eye.
1.37	Lens Power Modification (if applicable)	
Adjust the lens power if the subject's best sphere over-refraction is not plano. Additionally, for toric lenses, adjust the lens axis parameter if the settled lens orientation is such that a different axis would be more appropriate (use the LARS rule to determine the replacement lens axis).
 
For each power modification, select the adjusted fitting lens power as appropriate and repeat steps 1.33 through 1.36.
 
Up to two power modifications are allowed.

1.38	Lens Settling 2	Please wait a total of 10 minutes from final lens insertion to continue.
1.39	Visual Acuity	Record the best corrected Snellen distance visual acuity to the nearest letter (OD, OS, and OU). Subjects must read the smallest line until at least 50% of the letters are read incorrectly. Visual acuity with the study contact lenses must be 20/30 or better OD, OS and OU.

**Clinical Study Protocol**  
**Johnson & Johnson Vision**

Visit 1: Toric Lens Fitting: Phase 2		
Step	Procedure	Details
1.40	General Lens Fit Assessment	
Evaluate lens centration, movement on blink, and push-up test for each eye.
 
An unacceptable fit is deemed by one of the following criteria:
 
 
• limbal exposure at primary gaze or with extreme eye movement.
 
• edge lift.
 
• excessive movement in primary and up gaze.
 
• insufficient movement in all three of the following conditions: primary gaze, up gaze, and push-up test.
 
 
Note: if lens fit is unacceptable for either eye, the subject will be discontinued from the study.

1.41	Toric Fit Assessment (toric lenses only)	
Record for each eye:
 
 
1. The rotational position to the nearest degree
 
2. Lens stability with blinks
 
3. Toric fit acceptability. The toric lens fit will be designated as 'unacceptable' if either:
 
 
 
a. The lens ABSOLUTE ROTATION is greater than 20 degrees
 
b. The LENS STABILITY WITH BLINK is greater than 5 degrees
 
 
If one or both lenses demonstrate an unacceptable toric fit, the subject will be discontinued (proceed to final evaluation).

Visit 1: Treatment 1 Lens Fitting		
Step	Procedure	Details
1.42	Subject Reported Ocular Symptoms	Subjects will respond to a verbal open-ended symptoms questionnaire.

**Clinical Study Protocol**  
**Johnson & Johnson Vision**

Visit 1: Treatment 1 Lens Fitting		
Step	Procedure	Details
1.43	Continuance	
For the subject to continue in the study, they must meet all three of the following criteria:
 
 
• Distance visual acuity is 20/30 or better OD and OS.
 
• The lens fit is acceptable OD and OS.
 
• Investigator approval.
 
 
If the Investigator does not approve the dispensing of the first study lens, then the study is terminated for that subject.

1.44	Lenses Worn in Clinic	
The lenses will be released for approximately 2.5 hours for psychometric testing.
 
 
1. The subjects must wear both study lenses the entire time.
 
2. The lenses will be worn as daily wear only.
 
3. Rewetting drops are permitted if needed.
 
 
Note: In the event a lens is lost or damaged, it will be replaced immediately.

1.45	Psychophysical Testing Sequence	
The following psychophysical tests will be performed in any order:
 
 
1. Visual range (OU) at approximately 8 cpd 
 
a. Units: log relative energy
 
b. Range / decimal places: 0.00-10.00
 
 
 
2. Brightness perception (OU) 
 
a. Units: log relative energy
 
b. Range / decimal places: 0.00 to 10.00
 
 
 
3. Motion detection (OU) 
 
a. Units: mm
 
b. Range / decimal places: 0.00 – 700.00
 
 
 
 
Following the psychophysical testing by the principal investigator, the subject will return to the sub-investigator.

1.46	Lens Removal	The worn study lenses will be removed and discarded.

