# **Clinical Study Protocol**

## **Johnson & Johnson Vision**

### **4.2. Study Design Rationale**

The purpose of this study is to evaluate the performance of a new UV/HEV-filter in a 2x2 crossover design for three different subject groups (i.e., sphere wears, multifocal wears, and toric wears). Crossover designs are a well-established study design in which subjects are exposed to multiple treatments during different time periods. This design is cost effective and more efficient since it eliminates part of the inter-subject variability from the treatment comparisons. Subjects will be randomized into the two lens wear sequences: Test/Control or Control/Test. Randomization eliminates selection bias and balances both the known and unknown confounding factors that may affect the study outcomes. A potential limitation of crossover design is the carry-over effect from the previous treatment. The 2 study periods (visits) will be separated by 1-14 days and the wearing time of 2.5-3 hours in each period is considered effectively short to minimize the presence of the carry-over effect in the psychometric tests of interest. Rest period between trials within a single measurement type and between different measurement types is incorporated to eliminate the impact of any previous testing.

- Within a single measurement type (e.g., visual range), a minimum of 30-seconds will be taken between trials.
- Between measurement types (e.g., when switching from visual range to measuring brightness perception), a 5-minute break will be taken.
- Participants will be given a 15-minute break after every 45 minutes of visual function testing.

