##### Visual Range

The visual range metric will be analyzed separately for two of the three subject groups (i.e., Spherical wearers and Multifocal wearers) using a linear mixed model. The analysis will be conducted on the ITT population. An appropriate distribution from the exponential family (e.g., normal or lognormal) will be considered for the linear mixed modeling based on the distribution of the endpoint. The model will include lens type, lens sequence, and period as fixed effects. Other baseline and subject characteristics such as age, gender, race, and iris color will be included as fixed covariates when appropriate. An unstructured (UN) covariance matrix will be used to model the residual errors among within-subject repeated measures (R-side). If the model fails to converge, a Compound Symmetric (CS) matrix may be considered. The Kenward and Roger method will be used for the denominator degree of freedom.

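### Psychophysical test order is left free at each visit and not matched within a subject: a small, cheaply avoidable source of noise in the Test-Control difference

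*Combined protocol and SAP*

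**What the plan says.** The testing step is worded identically at both visits (Section 7.2, Step 1.45 at Visit 1 and Step 2.34 at Visit 2): "The following psychophysical tests will be performed in any order". Three tests follow: visual range, brightness perception and motion detection. Section 5.1 randomises the lens sequence only. No section fixes, randomises or counterbalances the test order, ties the second visit's order to the first, or asks for the order to be written down.

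Section 4.2 does deal with the effect of one test on the next. It says: "Rest period between trials within a single measurement type and between different measurement types is incorporated to eliminate the impact of any previous testing". The means are three rests: within a test type, "a minimum of 30-seconds will be taken between trials"; between test types, "a 5-minute break will be taken"; and "Participants will be given a 15-minute break after every 45 minutes of visual function testing". On session length, Steps 1.44 and 2.33 say: "The lenses will be released for approximately 2.5 hours for psychometric testing".

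For the primary analysis, Section 14.5 says: "The model will include lens type, lens sequence, and period as fixed effects". Age, gender, race and iris color may be added as covariates. There is no term for test order or position.

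**The concern.** Under the any-order rule, a subject can have visual range measured first with one lens and last with the other. If performance depends on position in the session, that difference falls inside the within-subject contrast on which the trial rests.

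The planned model cannot take it out. The period term absorbs only a shift shared by everyone at a visit, the sequence term describes lens order rather than test order, and the listed covariates do not change between a subject's two visits. If the order is not recorded, it cannot be adjusted for afterwards either.

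Three things could make position matter: fatigue, practice, and time on eye. The last arises because testing can begin soon after the 10-minute settling wait (Steps 1.22, 1.29 and 1.38) and then runs through a long wearing session, so position helps decide how long the lens has been in place when visual range is measured. Rests act on the first of these but not on the other two.

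What is at stake is the variance of the paired difference. The comparison with least room is visual range in multifocal wearers, a primary test.

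**Working it through.** **Inputs.** From Table 9 (Section 14.2), multifocal visual range: SD of paired differences 0.23, effect size 0.52, power 0.90, n = 41. Sphere visual range: SD 0.10. From the text of Section 14.2: one-sided alpha 0.025 for primary tests, an exact paired t-test, and 40 completers per group. The alpha of 0.05 in the table is read as the two-sided equivalent of 0.025 one-sided.

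**1. The plan's own figure.** Power = 1 − F(t_crit), where F is the noncentral t distribution with n − 1 degrees of freedom and noncentrality 0.52 × √n.
- n = 41 gives 0.901, so the stated 0.90 reproduces.
- n = 40, the planned completers, gives 0.894.

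The gap between 0.894 and 0.90 comes from 40 against 41 subjects, not from test order.

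**2. Which tests are sensitive.** At 40 completers, power is above 0.999 for sphere visual range and for sphere motion detection, and 0.979 for multifocal brightness perception. With 20% more variance the figures become above 0.999, 0.999 and 0.952. Only multifocal visual range has little slack.

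**3. Size of the order noise (assumed model).** Let each later position shift visual range by δ LRE, with orders random and independent at the two visits. Position is uniform on 1, 2, 3, with variance 2/3, so the difference between two visits has variance 2 × 2/3 = 4/3. The part of the paired-difference variance due to order is (4/3)δ². The documents give no value for δ.

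**4. Gain from matching the order.** Phase 2 repeats the Phase 1 procedures (Synopsis, Sample Size) and its assumptions come from Phase 1 data (Section 14.2). The order noise is therefore taken as already inside 0.23² = 0.0529, and matching removes it. The mean difference stays at 0.52 × 0.23 = 0.1196.

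| δ (LRE per position) | (4/3)δ² | Share of 0.0529 | Remaining variance | Power at n = 40 |
|---|---|---|---|---|
| 0 | 0 | 0 | 0.0529 | 0.894 |
| 0.02 | 0.0005 | 1% | 0.0524 | 0.897 |
| 0.05 | 0.0033 | 6% | 0.0496 | 0.912 |

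The gains are 0.897 − 0.894 = 0.003 and 0.912 − 0.894 = 0.018.

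**5. Plausibility limit on δ.** Sphere wearers take the same test under the same rule, and their total paired variance is 0.10² = 0.010. A δ of 0.10 would contribute (4/3) × 0.10² = 0.0133, more than that whole variance. It would also mean a shift of 2 × 0.10 = 0.20 LRE from first to last position, against a planned treatment effect of about 0.12. It is not used here. Even δ = 0.05 would take 0.0033/0.010, a third of the sphere variance. The sphere SD rests on about 10 Phase 1 subjects and multifocal wearers could differ, so this is a check on plausibility and not a bound.

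**The case against.** The strongest reply is that the plan already handles this. Section 4.2 lists rests at three levels, and Table 5 puts the whole of Visit 2 at 2.5 hours including fitting and slit lamp, so active testing is shorter than the wearing time suggests. This stands in part. The rests make a large fatigue effect less likely, and the documents do not show that any position effect remains. Rests still do not equalise practice or time on eye between the two visits.

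A second reply is that the independent-random-orders assumption is close to a worst case. If the site keeps a usual order, as a single site well might, the added variance is near zero. That stands, and it is why the figures above are illustrations.

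Two stronger readings are tempting, and the documents do not support either.
- **Power is lower than stated.** If order noise came on top of the planned SD, power at 40 would fall to 0.891 (δ = 0.02) or 0.875 (δ = 0.05). But Phase 1 ran under the same procedures and supplied the Table 9 inputs, so ordinary order noise is already in the 0.23.
- **The comparison is biased.** The person running the psychophysical tests is masked (Section 5.2), lens sequence is randomised (Section 5.1), and the protocol does not say who picks the order. No route to a systematic Test-Control difference is shown.

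Nor does free order undo what the crossover achieves. Section 4.2 justifies that design by its removal of part of the between-subject variation. Within-subject noise remains in any crossover; the point here is only that some of it can be avoided.

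**Conclusion.** The point holds as a minor one. The any-order rule is explicit at both visits, nothing matches or records the order, and the model cannot absorb a within-subject position difference. Any residual position effect is therefore avoidable noise.

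The benefit of removing it is efficiency only, and it matters mainly for multifocal visual range: about 0.3 to 1.8 percentage points of power at 40 completers. That range rests on a linear effect of 0.02 to 0.05 LRE per position, on independent random orders at the two visits, and on the Phase 1 SD already containing this noise. The true effect is not in the documents, and the gain may be close to nil.

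**What to change.** In Steps 1.45 and 2.34, replace the any-order wording with a requirement that each subject takes the three tests in the same order at Visit 2 as at Visit 1. Use either one common order for everyone or an order pre-assigned with the randomisation schedule, and record the order performed on the CRF. Additive position effects then cancel in the paired difference, and any departure from the assigned order can be seen and examined.

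The cost is one sentence in each of two steps, one CRF field and slightly less scheduling flexibility at the single site. The sample size and the analysis model need no change.

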**Clinical Study Protocol**  
**Johnson & Johnson Vision**

Visit 1: Treatment 1 Lens Fitting		
Step	Procedure	Details
1.47	Exit Slit Lamp Biomicroscopy	
FDA Slit Lamp Classification Scale will be used to grade the findings.
 
If the subject has a Grade 3 slit lamp finding, it will be recorded as an Adverse Event and the subject will be monitored as per the guidelines given in section 13.
 
If the clearance of the fluorescein needs to be expedited, preservative-free rewetting drops may be instilled.

1.48	Exit VA	Record the subject's distance visual acuity, OD, OS, and OU, to the nearest letter with their habitual correction in place.
1.49	Schedule next visit	Schedule the follow-up visit to occur within 14 days (counting the day of this visit as day 0, the subject may return on day 1 through 14).

**Clinical Study Protocol**  
**Johnson & Johnson Vision**

**VISIT 2**

Subjects will enter Visit 2 wearing the same form of habitual vision correction that they entered Visit 1.

Visit 2: Treatment 2 Baseline		
Step	Procedure	Details
2.1	Adverse Events and Concomitant Medications Review	Review any changes to the subject's medical history or concomitant medications from the previous study visit. Record any changes, and any adverse events.
2.2	Subject Reported Ocular Symptoms	Subjects will respond to a verbal open-ended symptoms questionnaire.
2.3	Visual Acuity	Record the distance Snellen visual acuity with the contact lenses (OD, OS, and OU) to the nearest letter. Subjects must read the smallest line until at least 50% of the letters are read incorrectly. 
 
• Note: Entrance visual acuity must be within 1 line of Visit 1 to continue. Otherwise, determine if there is an adverse event.
 

2.4	Slit Lamp Biomicroscopy	FDA Slit Lamp Classification Scale will be used to grade the findings. 
If the subject has a Grade 3 slit lamp finding, it will be recorded as an Adverse Event and the subject will be monitored as per the guidelines given in section 13.
 
If the clearance of the fluorescein needs to be expedited, preservative-free rewetting drops may be instilled.

2.5	Continuance	Verify that the subject is eligible to continue in the study. : 
Next step based on lens design:
 
 
• For spherical lenses, proceed to step 2.6.
 
• For multifocal lenses, proceed to step 2.14.
 
• For toric lenses, proceed to step 2.21.
 

**Clinical Study Protocol**  
**Johnson & Johnson Vision**

Visit 2: Spherical Lens Fitting: Phase 1 and 2		
Step	Procedure	Details
2.6	Lens Selection	
Assign the study lens (Test or Control) according to the randomization scheme provided by the biostatistician.
 
Select the contact lens power based on the vertex-corrected refraction or the final powers from Visit 1.
 
Record the test condition.

2.7	Lens Insertion	
The Investigator or the subject inserts the study lenses. Record the time of lens insertion.
 
Check for lens damage under the slit lamp before proceeding with lens settling.
 
Replace damaged lenses if applicable.
 
Ensure the subject is given a Patient Instruction Guide.

2.8	Lens Settling 1	Allow the study lenses to settle for a minimum of 5 minutes.
2.9	Subjective Best Sphere Over Refraction	Perform subjective best sphere refraction over the study lenses with a phoropter (adopt the maximum plus to maximum visual acuity (MPMVA) approach) and record the best corrected distance visual acuity to the nearest letter (OD, OS, and OU).
2.10	Lens Power Modification (if applicable)	
Adjust the lens power if the subject's best sphere over-refraction is not plano. For each power modification, select the adjusted fitting lens power as appropriate and repeat steps 2.6 through 2.9.
 
Up to two power modifications are allowed.

2.11	Lens Settling 2	Please wait a total of 10 minutes from final lens insertion to continue.
2.12	Visual Acuity	Record the best corrected Snellen distance visual acuity to the nearest letter (OD, OS, and OU). Subjects must read the smallest line until at least 50% of the letters are read incorrectly. Visual acuity with the study contact lenses must be 20/30 or better OD, OS and OU.

